^g Participants will be assessed at minimum daily, while hospitalized, for the occurrence of any clinical and adverse events (See [Section 8.2 Efficacy Assessments](#) and [Section 8.4 Adverse Events and Serious Adverse Events](#)) by the clinical care team as a part of standard of care. The clinical care team should inform the study team of any potential events. Additionally, the study team is expected to assess for the occurrence of potential events during scheduled study visits.

^h If hospital discharge occurs before Day 30, the PCFS should be performed the day after hospital discharge (up to 3 days after discharge allowed). A retrospective assessment of PCFS pre-COVID-19, which reflects functional status during the month preceding COVID-19 infection, should be performed after current PCFS assessment at hospital discharge.

Following hospital discharge, study activities may be performed remotely except for central laboratory blood collection.

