8.1.2 LABORATORY SAMPLES AND VALUES

Participants will have laboratory samples collected and analyzed both locally and centrally in accordance with the SoA.

Local Laboratory Values

Laboratory tests of interest listed below, obtained via the local laboratory that are used to assess eligibility*, or are collected during the participant's enrollment until hospital discharge or Day 30 visit (whichever is first) should be reported via the eCRF. In the case of D-dimer, initial value (eligibility) is preferred as collected at the time of hospital admission, prior to initiation of heparin treatment. In the case where a lab test is measured multiple times per day, the first scheduled values as well as any additional values that represent a clinically significant change should be reported.

- Hemoglobin
- D-dimer*
- White blood cell count (WBC)
- Platelet count*
- Estimated glomerular filtration rate (eGFR)*
- Aspartate aminotransferase (AST)
- Alanine aminotransferase (ALT)
- Total bilirubin
- Prothrombin time (PT)
- Partial thromboplastin time (PTT)
- Troponin
- Brain natriuretic peptide (BNP)

Central Laboratory Sample(s)

Central laboratory samples should be collected and shipped to the central laboratory as described in the Laboratory Manual. The following table outlines the samples that will be collected and analyzed via the central laboratory.

Table 2b. Central Laboratory Blood Collection

Day 1 ^a	Day 2 (24h post-dose)	Day 3 Phase 2b only	Day 8 ^b , or Day of Hospital Discharge (if prior to Day 8)	Day 30 Phase 2b only
Samples for clinical laboratory tests				
IL-6, hsCRP			IL-6, hsCRP	
D-dimer, PT, PTT, factor Xa tissue factor, antiphospholipid antibody	D-dimer, PT, PTT	D-dimer, PT, PTT	D-dimer, PT, PTT, factor Xa tissue factor, antiphospholipid antibody	antiphospholipid antibody
ADA for rNAPc2 subjects (Phase 2b only)	PK sample for rNAPc2 subjects (Phase 2b only)		PK sample for rNAPc2 subjects (Phase 2b only)	ADA for rNAPc2 subjects
Samples for future research use^c				
Future use serum and plasma aliquots and buffy coat			Future use serum and plasma aliquots	

^a Baseline Central Laboratory sample should be collected before administration of study medication (rNAPc2 or heparin). A sample up to 1-hour post-administration is acceptable.

^b For rNAPc2-allocated participants, Day 8 Central Laboratory samples should be collected before that day's dose of SoC thromboprophylaxis, if prescribed.

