 - The need for inpatient medical services should be assessed daily after randomization until the participant is discharged from the hospital, deceased, or Day 30 visit is reached.
 - Documentation pertaining to this assessment must be provided to the CEC as outlined in the Site Manual.
- Clinical events and adverse events assessment
 - Assess for the occurrence of any adverse events and report via the eCRF as appropriate. See [Section 8.4 Adverse Events and Serious Adverse Events](#) for more information about adverse events.
 - Assess for the occurrence of any clinical event that suggests the possibility that an efficacy outcome event has occurred. See [Section 8.2 Efficacy Assessments](#) for more information about clinical events of interest.
- Post-COVID functional status (PCFS) scale
 - PCFS scale may be performed remotely e.g. by telephone.
 - For patients discharged on Day 30, a retrospective assessment of PCFS pre-COVID-19, which reflects functional status during the month preceding COVID-19 infection, should be performed after current PCFS assessment.
 - PCFS scale assessments should be omitted if the patient remains hospitalized through Day 30 as the instrument is intended to assess outpatient recovery.
- Vital Status (alive or deceased)
- Healthcare Resource Utilization Assessment
- Central laboratory samples (Phase 2b only)

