9.3 POPULATIONS FOR ANALYSES

Randomized participants consist of all screened participants with randomization assignment, regardless of whether or not study intervention was administered. Participants treated without being randomized or treated before randomization will not be considered as randomized and will not be included in any analysis population. The safety experience of these participants will be reported separately, and they will not be included in the safety population.

The efficacy analysis population will be the intent-to-treat (ITT) population, consisting of all randomized participants as defined above. Participants in the ITT population will be analyzed according to the treatment group allocated by randomization.

An additional efficacy analysis population for sensitivity analyses of the primary efficacy endpoints will be the modified intent-to-treat (mITT) population, consisting of the subset of the ITT population that received at least one dose of study drug. Participants in the mITT population will be analyzed according to the treatment group allocated by randomization.

A per protocol population will include all participants who are randomized and receive all three doses of study drug post-randomization. Participants will be analyzed according to the treatment actually received.

The safety analysis population will be the safety population, consisting of the randomized population who received at least one dose or part of a dose of study treatment. Participants will be analyzed according to the treatment received (rNAPc2 or heparin).

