5.2 Analysis Populations and Scopes

All analyses are based on 2 elements:

- Analysis population, which specifies which participants will be included in an analysis; and
- Data scope, which specifies the time window within which data will be included in an analysis

Five analysis populations are defined for this study.

The **Intent-to-Treat (ITT) population** will include all participants who are randomized. Participants will be analyzed according to the treatment group allocated by randomization.

The **modified Intent-to-Treat (mITT) population** will include all participants who are randomized and received at least one dose of study drug. Participants will be analyzed according to the treatment group allocated by randomization.

The **Per Protocol population** will include all participants who are randomized, receive all three doses of study drug post randomization or receive SoC drug through day 7, have no major deviations from the protocol that affect the primary endpoint, and complete all pre-specified study assessments/activities. Participants will be analyzed according to the treatment actually received.

The **Safety population** will include all participants who are randomized and receive at least one dose or part of a dose of study treatment post-randomization. Participants will be analyzed according to the treatment actually received.

The **All Screened population** will be defined as all participants with any data entered into the database.

The analysis populations will be listed by participant.

The ITT, mITT and Per Protocol data scope includes outcomes and events observed from a given participant’s date of randomization until either their final or Day 30 contact, determined by whichever occurs first. This will be applied mainly to the analyses of efficacy endpoints.

The ITT, mITT and Per Protocol data scope will also be used for the secondary safety endpoints of major or non-major clinically relevant bleeding through Day 30 and any bleeding through Day 30.

The on-treatment data scope will include all outcomes and events observed from randomization until 72 hours following permanent discontinuation of the study drug. This on-treatment data scope will be applied mainly to the analyses of safety endpoints.

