8.3 Laboratory Data

A summary of laboratory (Central Laboratory) values (e.g., AST, ALT and bilirubin) outside normal limits (i.e., either above the ULN or below the lower limit of normal (LLN) where limits are defined), as well as a summary of any participant potentially meeting the criteria for Hy's law will be provided where Hy's Law criteria will be defined as: AST or ALT > 3× ULN and total bilirubin > 2× ULN at any time during the study.

9 Interim Analyses

Additional details of these analyses will be described in the DSMC Charter.

10 Composite and Net Endpoints

Composite endpoints will first be analyzed as an aggregate and then component-wise, as discussed in the context of modeling clinical events in [Section 7.2.3](#). The primary approach to net outcomes will be to perform them in all randomized patients in the 30-day study period.

Composite/net clinical outcomes include the combination of irreversible harm and efficacy outcomes, including:

- All-cause mortality, thrombotic events, initiation of organ support, rehospitalization adjudicated as to its relatedness to COVID-19.

11 Subgroup and Sensitivity Analyses

The sensitivity analyses will be performed on the ITT, mITT, and Per Protocol populations.

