11.3 Secondary Efficacy Endpoint Subgroup and Sensitivity Analyses

Secondary efficacy endpoints will be subject to the same sensitivity and subgroup analyses as the primary efficacy endpoints.

The following laboratory parameters will be collected and analyzed by a central laboratory. Change from baseline to both Day 8 or discharge will be summarized for inflammatory biomarkers (IL-6, hsCRP) and coagulation biomarkers (PT, PTT, factor Xa and tissue factor). All data will be listed. Analyses will be by generalized linear mixed effects models as described above for sensitivity and subgroup in the primary efficacy endpoint. For purposes of interpretation of outcomes, IL-6 and hsCRP are considered measures of systemic inflammation, PT, PTT and factor Xa are coagulation parameters, and tissue factor is the biologic target of rNAPc2. In addition, in a subset of participants anti-phospholipid antibodies known to be generated in COVID-19 and inhibited by rNAPc2, are being measured at baseline, Day 8/discharge and on Day 30 at a specialty laboratory.

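### The SAP's Per Protocol set requires every scheduled assessment to be completed, so membership can turn on events after the Day 8/discharge endpoint

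*SAP*

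**What the plan says.** SAP 5.2 sets four conditions for the Per Protocol set: randomization; all three rNAPc2 doses, or standard-of-care drug through Day 7; and then that participants "have no major deviations from the protocol that affect the primary endpoint, and complete all pre-specified study assessments/activities". The protocol's definition (9.3) has no completion condition: "A per protocol population will include all participants who are randomized and receive all three doses of study drug post-randomization". Protocol 9.4.1 lets the SAP prevail where the two differ. SAP Section 12, which lists changes from the protocol's methods, does not mention this one.

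The set is used beyond listings. SAP Section 7 bases efficacy on ITT and refers the mITT and Per Protocol analyses to Section 11, which states: "The sensitivity analyses will be performed on the ITT, mITT, and Per Protocol populations". SAP 11.3 adds: "Secondary efficacy endpoints will be subject to the same sensitivity and subgroup analyses as the primary efficacy endpoints". Some baseline and exposure summaries (SAP 6.2 to 6.3) also use it.

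On the schedule, Protocol 8.1.1 and 8.1.3 include a Day 30 central laboratory sample in Phase 2b. A footnote to the schedule says: "Following hospital discharge, study activities may be performed remotely except for central laboratory blood collection".

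**The concern.** The deviation condition is confined to deviations that bear on the primary endpoint. The completion condition beside it is not. The primary endpoint (SAP 2.4.1) is finished at Day 8 or earlier discharge, yet the pre-specified assessments run to Day 30. A participant could have every dose and a valid endpoint D-dimer and still be dropped because of something that happened up to three weeks later.

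Those later events are not neutral. Death may depend on treatment, and the protocol justifies D-dimer as an endpoint partly because it predicts survival (Protocol Section 3). Selecting on survival and on return for a blood draw can therefore bias the Per Protocol D-dimer comparison. The effect on the clinical endpoints is more direct. All-cause death is a component of the secondary composite (SAP 7.2.3). The time-to-recovery analysis (SAP 7.2.2) keeps deaths in the risk set as non-recoveries by censoring them after the longest observation window. A Per Protocol set with few or no deaths would defeat both provisions.

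**Working it through.** No Per Protocol size is stated, so there is no plan figure to reproduce. The check is mainly textual.

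1. **Scope of the condition.** SAP 5.2 runs the Per Protocol data scope to the final or Day 30 contact, whichever is first. Nothing confines completion to Day 8.

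2. **Which Day 30 items can be completed after a death?** Vital status can: Protocol 8.1.3 records alive or deceased. PCFS can: Protocol 10.4 has a death grade. Daily ACTT stops at death by design (Protocol 8.1.1). The Day 30 central sample cannot be given, and no exemption for death is written.

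3. **Which items can a discharged survivor miss?** Day 30 contact may be remote, but the sample may not. A survivor reached only by telephone has not completed all activities.

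4. **Is the sample required in both arms?** Protocol Table 2b lists two Day 30 tests: antiphospholipid antibody, with no arm limit, and "ADA for rNAPc2 subjects". SAP 7.2.4 measures antiphospholipid antibody only in a subset. For a heparin participant outside that subset, it is arguable that no Day 30 draw is pre-specified. For every rNAPc2 participant one is.

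5. **Illustration of size.** The planned evaluable number is 160 × (1 − 0.20) = 128, matching the power table (128) and the text (about 130). Let d be the share of these dying after the endpoint sample and before the Day 30 sample, and m the share of survivors missing the draw. Both are assumptions. Remaining = 128 × (1 − d) × (1 − m).

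| d | m | Remaining | Removed |
|---|---|---|---|
| 5% | 5% | 128 × 0.95 × 0.95 = 115.5 | 12.5 |
| 10% | 20% | 128 × 0.90 × 0.80 = 92.2 | 35.8 |
| 15% | 40% | 128 × 0.85 × 0.60 = 65.3 | 62.7 |

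For given d and m these are upper figures. Some of the 128 would already fail the dosing or deviation condition, and the table assumes the draw is required of everyone.

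6. **If the draw binds only rNAPc2.** Under 1:1:2 allocation, pooled rNAPc2 is half of 128, or 64. With d = 10% and m = 20%, 64 × 0.90 × 0.80 = 46.1 remain, so about 18 are removed. If no heparin participant is in the antiphospholipid subset, none is removed for want of the Day 30 draw. This is the extreme case of the arm difference in step 4.

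**The case against.** The strongest reply is that the sponsor meant all applicable assessments. There is support for this. Several items are conditional by design: ACTT ends at death, and PCFS is omitted for patients still in hospital at Day 30. The Per Protocol data scope allows a final contact before Day 30. SAP 11.1 plans multiple imputation for all types of missingness, and on the literal reading little would be left to impute in this set. That reading would keep the deaths. It would not keep discharged survivors who miss the draw, because the draw applies to them. Nor does the SAP state it, so two programmers could build different sets.

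It is also fair that Per Protocol sets always select on post-randomization events, that no decision rule depends on this one, and that the same analyses run on ITT and mITT, which keep deaths. This limits the consequence but does not justify selecting on events after the endpoint is measured.

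A reader might infer three stronger things that the documents do not support:

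- That a participant who dies cannot complete any Day 30 item. Vital status and PCFS can both be recorded; only the sample cannot.
- That the set contains no deaths by construction. This follows only from the literal reading.
- That losses can be counted by applying a death rate to the 80 randomized per side (5%, 10% or 20% giving 4, 8 or 16), plus about 15 missed draws in each (76 × 0.20). The documents give neither rate. Those counts include participants who already fail the dosing condition, treat all survivors as discharged with complete D-dimer, and assume the draw is required of every heparin participant.

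**Conclusion.** The point holds as a defect in the Per Protocol definition. As written, the completion condition selects on events after the primary endpoint, may bear unequally on the arms, and departs from the protocol's definition without being declared. On the literal reading the Per Protocol D-dimer, time-to-recovery and composite sensitivity analyses would have few or no deaths. On the more generous reading they would still lose survivors who miss the Day 30 draw. The primary conclusion is not at risk, since neither the ITT primary analysis nor the ITT and mITT sensitivity analyses depend on this set. The size is unknown: the illustration of about 13 to 63 of 128 rests wholly on assumed death and missed-draw rates and overstates the additional loss for those rates. The change should be made before unblinding, but it is not critical.

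**What to change.** In SAP 5.2, for the D-dimer analyses, replace the completion condition with a requirement for a valid baseline and Day 8 (or discharge, if earlier) D-dimer. Define valid by the sampling rules in SAP 7.1.1 and say whether a carried-forward value under SAP 5.1 qualifies. State that death, or a missed assessment after the primary endpoint measurement, does not exclude a participant. State separately how deaths before any Day 8/discharge sample are handled in the Per Protocol time-to-recovery and composite analyses; a D-dimer requirement alone would leave that open. List the departure from Protocol 9.3 in SAP Section 12.

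Once both D-dimer values are required, imputing the primary endpoint within this set has little purpose, and SAP Section 11 could say so. The cost is a few sentences in the SAP before unblinding, with no new data and no change to trial conduct.

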4.4 END OF STUDY DEFINITION

Participants will complete their study participation after their final or Day 30 contact. The end of the study is defined as completion of the last enrolled participant's final visit or contact.

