7.3 LOST TO FOLLOW-UP

All randomized participants will be followed for outcomes until Day 30 whether study medication has been continued or discontinued. Only if a participant withdraws consent for all follow-up (active and passive) will they be considered to have withdrawn consent. If a participant cannot be contacted or has requested no contact, site staff will ascertain clinical endpoint events through the patient's physician or electronic medical record. A participant will be considered lost to follow-up if he or she is unable to be reached by the study site staff and no information from external sources (e.g. treating physicians, electronic medical record, family, registries) can be obtained. Only participants for whom no information can be ascertained, will be considered lost to follow-up.

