- Central laboratory samples, if not already collected at Day of Hospital Discharge

Day of Hospital Discharge

The following procedures will occur on the Day of Hospital Discharge:

- Concomitant medication (may be obtained/extracted from the medical record to minimize staff exposure to COVID-19)
- Study medication administration, if applicable
- Local laboratory values, if applicable
- Assess need for inpatient medical services and complete ACTT
 - The need for inpatient medical services should be assessed daily after randomization until the participant is discharged from the hospital, deceased, or Day 30 visit is reached.
 - Documentation pertaining to this assessment must be provided to the CEC as outlined in the Site Manual.
- Clinical events and adverse events assessment
 - Assess for the occurrence of any adverse events and report via the eCRF as appropriate. See [Section 8.4 Adverse Events and Serious Adverse Events](#) for more information about adverse events.
 - Assess for the occurrence of any clinical event that suggests the possibility that an efficacy outcome event has occurred. See [Section 8.2 Efficacy Assessments](#) for more information about clinical events of interest.
- Post-COVID functional status (PCFS) scale
 - If hospital discharge occurs before Day 30, PCFS assessment should be performed the day after hospital discharge (up to 3 days after discharge allowed).
 - PCFS scale may be performed remotely e.g. by telephone.

- A retrospective assessment of PCFS pre-COVID-19, which reflects functional status during the month preceding COVID-19 infection, should be performed after current PCFS assessment at hospital discharge.
- Healthcare Resource Utilization Assessment
- Central laboratory samples, if Day of Hospital Discharge is prior to Day 8

Day 30 Visit (+/- 3 Days)

The following procedures will occur at the Day 30 visit:

- Visit procedures other than central lab assessment may be performed remotely for participants who have already been discharged from the hospital
- Concomitant medication (may be obtained/extracted from the medical record to minimize staff exposure to COVID-19)
- Study medication administration, if randomized to heparin and still hospitalized
- Local laboratory values, if applicable
- Assess need for inpatient medical services and complete ACTT

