summarized by Kaplan-Meier estimates. Additionally, a treatment hazard ratio and corresponding 95% confidence interval will be estimated by a Cox proportional hazard model stratified by local laboratory D-dimer level at screening.

In the analysis of the primary efficacy endpoint, participants who die within 30 days of randomization will be censored at Day 30. In addition, participants surviving to Day 30 who have not met the criteria for recovery by the time of their last ACTT scale assessment on or prior to Day 30 will be censored on the day of their last assessment. There will be no censoring prior to Day 30 due to study treatment discontinuation, initiation of non-study treatment, or intermittently missed ACTT scale assessments.

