4.3 Determination of Study Day

The day the participant is randomized will be considered study “Day 1.” The day prior to randomization will be considered study “Day -1.” There will be no Day 0. If the start day is missing the first day of the month will be used.

If the start year or stop year is missing it is assumed the medication was taken concomitantly with study drug.

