7.2.2 Time to Recovery

Time to recovery by Day 30, with Day 1 being the date of randomization. Recovery is defined as the first day a participant meets criteria for category 6, 7, or 8 of the ACTT ordinal scale. The analysis of time to recovery will be a comparison of the combined rNAPc2 dose groups vs. SoC heparin by a stratified log-rank test, where stratification is according to local laboratory screening D-dimer level \leq or $> 2 \times$ local laboratory ULN. Cumulative incidence by treatment group will be summarized by Kaplan-Meier estimates. Additionally, a treatment hazard ratio and corresponding 95% confidence interval will be estimated by a Cox proportional hazard model stratified by local laboratory D-dimer level at screening. In addition, the two rNAPc2 dose groups will be compared for time to recovery.

Participants who die within 30 days of randomization will be censored at the day $x+1$, where x denotes the longest observation window among all subjects in the analysis. In addition, participants surviving to their Day 30 visit who have not met the criteria for recovery by the time of their last ACTT scale assessment on or prior to the Day 30 visit will be censored on the day of their last assessment on or prior to the Day 30 visit. There will be no censoring prior to Day 30 due to study treatment discontinuation,

initiation of non-study treatment, or intermittently missed ACTT scale assessments. Patients lost to follow-up or otherwise of unknown status occurring prior to Day 30 will be censored based on, and at the day of, the last known status.

The frequency and percentage of participants with each recovery category (ACTT equal to 6, 7, or 8) will be summarized.

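### The Phase 2b data scope ends at a contact that may fall as early as Day 27, so 30-day endpoints analysed without censoring can lose events on Days 28 to 30

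*SAP*

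**What the plan says.** **Scope.** SAP 5.2 (Analysis Populations and Scopes) runs the ITT, mITT and per-protocol scope from randomization "until either their final or Day 30 contact, determined by whichever occurs first". It applies the same scope to both secondary endpoints of bleeding through Day 30.

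**Timing of the contact.** Protocol 8.1.3 has a "Day 30 Visit (+/- 3 Days") and Table 2a gives the same window. Under Protocol 4.4, "Participants will complete their study participation after their final or Day 30 contact". SAP 4.3 sets the origin: "The day the participant is randomized will be considered study" Day 1.

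**Cut-off wording.** The documents do not use one cut-off:
- Protocol 7.3: "All randomized participants will be followed for outcomes until Day 30 whether study medication has been continued or discontinued".
- Table 2a continues daily ACTT scoring until discharge, death or Day 30. The visit descriptions in Protocol 8.1.3 continue it until the participant is discharged, "deceased, or Day 30 visit is reached".
- For unrecovered survivors, Protocol 9.4.2 (Phase 3) refers to the "last ACTT scale assessment on or prior to Day 30 will be censored". SAP 7.2.2 uses the "last assessment on or prior to the Day 30 visit".
- SAP 8.2.3 collects adverse events to the later of Day 30 and final contact, whereas SAP 5.2 takes the earlier of two contacts.

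**Endpoints and models.** The secondary composite covers 30 days (SAP 2.5.1) and is analysed by logistic and Poisson regression with no offset for follow-up time (SAP 7.2.3). Bleeding through Day 30 is a count and percentage (SAP 8.2). Organ-support-free days may be grouped with a category of exactly 30 (SAP 7.3.2). ACTT of 6 or more by Day 30 is a secondary endpoint (SAP 2.5.1), and SAP 7.2.1 gives secondary endpoints the same analysis as the primary, which has no censoring.

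**The concern.** The endpoints are defined over a fixed 30 days, but the scope is tied to a contact whose date can vary by up to six days between compliant participants. Where the method has no censoring and no exposure term, the analysis cannot tell a participant who was event-free through Day 30 from one who was event-free only through Day 27.

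A death, thrombosis, readmission or bleed on Day 28 after a Day 27 contact is then outside the scope even though it lies inside the endpoint's own definition. The same participant has at most 27 observed organ-support-free days. Without a stated rule, that participant cannot enter the 30-day category, and a Day 28 death would not bring the score of -1.

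At stake are the accuracy of the 30-day secondary and exploratory results and whether two programmers would derive the same cut-off. The primary conclusion does not depend on this.

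**Working it through.** **1. Window.** The visit is Day 30 with three days either side (Protocol 8.1.3 and Table 2a).
- Earliest contact: 30 - 3 = Day 27. Latest: 30 + 3 = Day 33.
- Days out of scope after a Day 27 contact: 28, 29 and 30, so 3/30 = 10%.
- Largest difference in scope between two participants seen in window: 33 - 27 = 6 days.

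**2. The one stated figure that rests on 30 days.** Protocol 9.2 expects 360 recovery events from 450 Phase 3 participants, randomized 1:1, with medians of 11 and 15 days. With exponential recovery:

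events by day t = 225 x [(1 - 2^(-t/11)) + (1 - 2^(-t/15))]

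- t = 30: 225 x (0.849 + 0.750) = 359.8, which reproduces 360. The protocol's own arithmetic therefore takes exactly 30 days of follow-up for everyone.
- t = 27: 225 x [(1 - 0.182) + (1 - 0.287)] = 344.3, or 4.3% fewer.

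This shows how sensitive a 30-day count is to the window. It does not measure bias here: recovery is censored, the figures are Phase 3 assumptions, and Phase 3 has a separate analysis plan (SAP 1).

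**3. Endpoints without censoring.** The documents give no 30-day event risks for Phase 2b, so a range is assumed. With a constant hazard and 30-day risk p, the risk seen by Day 27 is 1 - (1 - p)^(27/30). The last column multiplies the loss by 160 participants and takes the extreme case of every contact on Day 27.

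| Assumed 30-day risk | Seen by Day 27 | Loss (points) | Participants of 160 |
|---|---|---|---|
| 5% | 4.51% | 0.49 | 0.8 |
| 10% | 9.05% | 0.95 | 1.5 |
| 20% | 18.19% | 1.81 | 2.9 |
| 40% | 36.86% | 3.14 | 5.0 |

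The loss is smaller if events come early in the admission, or if only some contacts are early.

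**4. Which endpoints are exposed.**
- Exposed: the secondary composite (SAP 7.2.3), bleeding through Day 30 (SAP 8.2) and organ-support-free days (SAP 7.3.2).
- Exposed for inpatients only: ACTT of 6 or more by Day 30. Categories 7 and 8 are both out of hospital, so anyone alive and not yet recovered on Day 27 is an inpatient. Table 2a keeps scoring that person to Day 30, while the visit text and SAP 5.2 stop at the contact.
- Handled by censoring: time to recovery (SAP 7.2.2), and mortality and mortality or thrombosis (SAP 7.3.1, also capped at Day 30).
- Not affected: the primary efficacy and primary safety endpoints, both at Day 8.

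**The case against.** The strongest reply is that the plan already intends follow-up to Day 30. Protocol 7.3 says so for all randomized participants, Table 2a scores inpatients daily to Day 30, SAP 8.2.3 takes the later date for adverse events, and SAP 10 places net outcomes in the 30-day study period. On this view SAP 5.2 is only an outer limit and the endpoint definitions govern.

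Much of this stands. It rules out several stronger readings that a reader might infer:
- *That every 30-day endpoint is affected.* The time-to-event endpoints censor an early contact; they do not score it as a final status.
- *That data collection closes on Day 27.* The texts conflict on this, and several point to Day 30.
- *That other participants are counted to Day 33.* No passage says so. SAP 7.3.1 excludes it for mortality and mortality or thrombosis, and the other endpoints are worded to Day 30. Only the scope in SAP 5.2 and the recovery censoring phrase in SAP 7.2.2 leave room for later data.
- *That staff who know the allocation bias the result through the contact date.* Sites do know the assignment (Protocol 6.3), but the window is the same in every arm and nothing shows differential timing.

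The reply does not remove the gap. SAP 5.2 states which data enter the analysis, and it names the earlier contact. A discharged participant seen on Day 27 has no later scheduled contact, so the intention in Protocol 7.3 has no visit behind it. Multiple imputation (SAP 11.1 and 11.3) is a sensitivity analysis, and nothing flags Days 28 to 30 as missing for such a participant.

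**Conclusion.** The point holds for the Phase 2b endpoints that cover 30 days and are analysed without censoring or an offset. For them, SAP 5.2 can exclude up to 3 of 30 days, and an outcome in those days would by default count as absent. For ACTT of 6 or more by Day 30 this assumes that SAP 7.2.1 applies; if that probability is read from the censored curve in SAP 7.2.2, an early contact is handled there.

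The effect is likely small. With assumed 30-day risks of 5% to 40% and a constant hazard, the loss is 0.49 to 3.14 percentage points even if every contact fell on Day 27. The distribution of contact dates is unknown. No difference between arms is shown, and the Day 8 primary endpoints stand as they are.

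Separately, the cut-off wording is inconsistent within and between the two documents and should be reconciled. This is a worthwhile improvement and does not threaten the trial's main result.

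**What to change.** - **SAP 5.2 and 7.2.2:** end the data scope at study Day 30 for all participants, in place of the contact or visit, and align this with the collection rule in SAP 8.2.3.
- **Protocol Table 2a and 8.1.3:** schedule the final contact from Day 30 to Day 33 (0/+3 days), and continue inpatient ACTT through study Day 30, as Table 2a already has it.
- **Contacts already made on Days 27 to 29:** confirm status through Day 30 from the medical record. Protocol 7.3 already uses this source for participants who cannot be contacted or who ask not to be. Where status cannot be confirmed, state the rule (for example, an offset for observed days in the Poisson model, or treatment as missing) so that it does not default to no event.

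The SAP edit alone does not recover unobserved days; the window change or the record check must go with it.

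**Cost.** The SAP changes are a few phrases. The window change needs a protocol amendment, and sites lose three days of early scheduling flexibility. The latest visit stays at Day 33, so the stated participant duration of up to 40 days does not change.
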